### **7.2. Secondary Outcome Variables – Efficacy**

Secondary efficacy variables will include mean change from baseline scores of the YBOCS and WHO Adult ADHD Self-Report Scale inventories. Response as defined by a 20% decrease from baseline will also be calculated.

### **7.3. Safety Analysis**

Safety will be assessed by recording the frequency and severity of adverse events, defined as any new symptom or worsening of a pre-existing symptom. Adverse events reported on case report forms will be mapped to preferred terms and body systems using the Medical Dictionary for Regulatory Activities (MedDRA) coding dictionary. The number and percent of subjects reporting each event will be summarized during the study period. Incidence of adverse events by maximum reported severity will also be tabulated. Serious adverse events and adverse events leading to discontinuation will be displayed.

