#### **4.3. Visit 1 – Baseline Visit #1**

After the subject has been determined to have decision-making capacity to provide informed consent, the following assessments must be conducted at Visit 1:

- Written informed consent
- Review inclusion and exclusion criteria
- Detailed medical history including review of medical records, current medications and duration of prior TS medication trials
- DSM-IV SCID to determine subject has diagnosis of TS by one study psychiatrist or neurologist (first evaluator), for ages 15-17 this will be the K-SADS assessment.
- Complete physical examination including height, weight and vital signs

Date: 2/24/2021

Principal Investigator: [name], PhD

Application Number: NA\_00073086

- EKG, blood samples (CBC, and complete metabolic panel) for clinical laboratory tests
- Urine sample for urine toxicology screen and urine pregnancy test (for females)
- TS symptom scales, including the Yale Global Tic Severity Scale (YGTSS), the Yale-Brown Obsessive Compulsive Scale (YBOCS) for OCD symptoms, and the WHO Adult ADHD Self-Report Scale (ASRS) for ADHD symptoms.
- Assessment of depression, anxiety, or symptoms of mania using the Hamilton Depression Rating Scale (Ham-D), the Beck self-reporting Anxiety Inventory (BAI), and the Young Mania Rating Scale (YMRS). For ages 15-17, the Ham-D and BAI scales will be replaced with the Beck Youth Inventory.
- Columbia Suicide Severity Scale (CSSS).
- Neurocognitive battery – consisting of the Grooved Pegboard test, the Judgment of Line Orientation, the Trailmaking Test (A&B), the Hopkins Verbal Learning Test, and the Verbal Fluency test (COWAT). And for this visit only, the Mini-Mental State Examination (MMSE), the Wechsler Abbreviated Scale of Intelligence (WASI), and the Brief Visuospatial Memory Test – Revised (BVMT-R). (20)
- Subject to be referred to his/her medical physician for a pre-operative evaluation to determine if safe to undergo surgery and anesthesia
- Global Assessment of Function (GAF, DSM-IV Axis V) of no more than 50 (to demonstrate that subject's condition is severe and disabling)
- At the conclusion of this visit, all subjects who meet all inclusion/exclusion criteria will be given an appointment card for the next study visit.

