The subject will come in for four further follow-up visits weekly after the initial programming session (Visit #6). The study neurologist experienced in programming in conjunction with one of the study psychiatrists will use TS symptom scales (especially YGTSS), acute changes in OCD or ADHD symptoms, acute changes in depression or anxiety symptoms, and/or appearance of adverse events deemed likely to be related to DBS to optimize programming at all subsequent follow-up visits.

The following assessments will be conducted:

- Programming Form
- New/changed adverse events
- Record changes in concomitant medications
- TS symptom scales ( YGTSS, YBOCS, WHO ASRS)
- Ham-D, BAI, and YMRS for depression, anxiety, and/or mania symptoms (Beck Youth Inventory for ages 15-17)
- CSSS at alternating visits.
- Global Assessment of Function Scale (GAF)
- Neurocognitive battery (as per Visit #1)

At the conclusion of this visit, the subject will be given an appointment card for the next study visit.

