### **7.4. Statistical Plan**

This is a pilot study looking at using DBS in 10 Tourette Syndrome patients.

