### **7.5. Early Stopping Rules**

Date: 2/24/2021

Principal Investigator: [name], PhD

Application Number: NA\_00073086

DBS will be discontinued if the subject experiences a worsening of his tic or other Tourette symptoms (or OCD, ADHD, depression, or anxiety symptoms) without returning to baseline (prior to DBS implantation) within 4 weeks from the worsening of the symptoms. DBS will be discontinued if subjects experience suicidal ideation or mania that does not improve with turning off the stimulator. DBS will also be discontinued if neurologic symptoms including muscle contractions, flashing lights, electric jolting sensations, increase in dyskinesias will not improve with stimulator setting change and they are severe enough to interfere with patient daily functioning. Finally DBS will be discontinued if subjects are unable to tolerate the stimulator for any reason not foreseen by the investigator and that clearly interferes with subject's functioning.

Subjects will also be removed from the study for any significant adverse events that jeopardize patient safety. This includes any events related to the surgical procedure or subsequent DBS stimulation therapy. The entire study of 10 subjects will be stopped should the number of subjects meeting the above **Early Stopping Rules** reaches 3 at any point in the study. If this occurs before the full subject recruitment goal has been met, no further subjects will be recruited.

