### **8.3. Plans for reporting unanticipated problems or study deviations**

The PI of the study will be responsible for reporting all adverse events to the IRB. Serious adverse events deemed to be associated with the study device (adverse device effect) will be reported to the IRB within 7 days. Any deaths will be reported within 24 hours.

Adverse device effects (ADEs) in this study are identified and categorized in a way patterned after the Code of Federal Regulations (21 CFR 812.3):

a. An adverse device effect (ADE) is any serious adverse effect on the health and/or safety or any life threatening problem or death caused by, or associated with the device and/or stimulation therapy if that effect, problem or death was not previously identified in nature, severity, or degree of incidence in the application; or any other unanticipated serious problem associated with a device that relates to the rights, safety, or welfare of subjects (21 CFR 812.3):

- i. The implanted components (lead, extension, neurostimulator)
- ii. The lead/extension tract or neurostimulator pocket
- iii. The burr hole site

b. An event will not be considered related to the device when it is the result of:

- i. A preexisting medical condition
- ii. A medication

Furthermore, AEs will be further categorized and identified as Surgical/Procedure Related, Device Related, Therapy Related, Disorder Related, or Other/Procedure Related. Examples of each of these categories may include (but are not limited to):

Surgical/Procedure Related – surgical site infection, perioperative mental status changes, perioperative confusional state or delirium, perioperative syncope, perioperative adverse drug reactions, cerebral hemorrhage, perioperative stroke, perioperative pulmonary embolism, etc.

Date: 2/24/2021  
Principal Investigator: [name], PhD  
Application Number: NA\_00073086

Device Related – Lead fracture, lead migration, implantable pulse generator failure or abnormal function, skin erosion or delayed infection, etc.

Therapy Related – gait disturbance or balance disorder, confusional state or delirium not attributable to medication or other health problem, mental status changes not attributable to medication or other health problem, problems with speech, depression and suicidal ideation, induced dyskinesias, etc.

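### Depression, anxiety, mania and suicidality scales are scheduled throughout but have no planned summary, so a score shift can miss the safety result

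*Combined protocol and SAP*

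**What the plan says.** Section 2.1 makes safety one of two primary objectives. Section 7.3 sets out the analysis: "Safety will be assessed by recording the frequency and severity of adverse events, defined as any new symptom or worsening of a pre-existing symptom". The events come from case report forms and are coded in MedDRA. They are reported as numbers and percentages of subjects and by maximum severity, with serious events and events leading to discontinuation displayed.

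Section 7.2 reads: "Secondary efficacy variables will include mean change from baseline scores of the YBOCS and WHO Adult ADHD Self-Report Scale inventories". It adds a 20% response definition. Section 7.1 covers the tic scale. Section 7.4 is a single sentence: "This is a pilot study looking at using DBS in 10 Tourette Syndrome patients".

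The psychiatric scales are rated repeatedly. Section 4.8 lists, for Visits 6 to 9, "Ham-D, BAI, and YMRS for depression, anxiety, and/or mania symptoms (Beck Youth Inventory for ages 15-17"; Sections 4.3 to 4.5, 4.7, 4.9 and 4.10 list the same instruments, and the CSSS is added at some visits.

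The protocol also treats these symptoms as possible harms. The examples of therapy-related events in Section 8.3 include "problems with speech, depression and suicidal ideation, induced dyskinesias, etc". Section 7.5 states: "DBS will be discontinued if subjects experience suicidal ideation or mania that does not improve with turning off the stimulator". It also makes unresolved worsening of depression or anxiety a ground for discontinuation, and three subjects meeting its rules stop the study.

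**The concern.** The safety analysis and the safety measurements do not meet. The scheduled scales are the trial's only scored data on depression, anxiety, mania and suicidality, and Section 7.5 makes these symptoms grounds for discontinuation. Section 7.3, followed as written, does not use the scores.

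A change on a scale reaches the safety tables only if someone also enters it as an adverse event, and no rule says when that must happen. In an open-label study where the same team rates the scales and adjusts the stimulator, a change can be met by a new setting and leave no trace in the reported safety result. If no summary is fixed in advance, the choice of which scales to report, and how, would also be made after the scores are known.

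**Working it through.** The plan states no figure on this point, so there is none to reproduce. The check is a count, a reading of the analysis sections, a trace of how a score could reach the safety tables, and the precision of the proposed summaries.

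**1. Scheduled ratings.** Visits are taken from table 4.12; N = 10 from Sections 5.1 and 7.4.

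| Scale | Baseline visits | Visits after lead implantation | Total |
|---|---|---|---|
| Ham-D, BAI, YMRS (each) | 1, 2, 3 (3) | 5 to 13 (9) | 12 |
| CSSS | 1, 3 (2) | 6, 8, 10, 12 (4) | 6 |

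- All ratings: 10 × (3 × 12 + 6) = 420.
- After lead implantation: 10 × (3 × 9 + 4) = 310.
- From Visit 6 on: 10 × (3 × 8 + 4) = 280.

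These counts assume 10 adults who attend every visit. At ages 15-17 one inventory replaces Ham-D and BAI. Unscheduled visits (Section 4.13) and long-term follow-up (Section 4.14) would add ratings.

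**2. Where the scores are analysed.** Section 7.1 uses the YGTSS, 7.2 the YBOCS and ASRS, 7.3 adverse events, and 7.4 nothing specific. Section 7.5 uses the symptoms for stopping but names no scale and no cutoff. So 0 of the 420 ratings have a stated summary.

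**3. From score to safety table.** Section 4.8 lists acute changes in depression or anxiety and the appearance of adverse events as separate items, either of which may prompt a change in settings. Sections 4.9 and 4.10 repeat the separation. A mood or anxiety change can therefore be acted on without being classed as an event. Mania is not named among those prompts; for the YMRS the gap is simply that no text turns a score into an event or a summary.

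**4. Visit 5.** Section 4.8 identifies Visit 6 as the initial programming session. Table 4.12 marks programming at Visit 5 as well. Until these passages are reconciled, Visit 5 cannot safely be grouped with the stimulation visits.

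**5. What summaries could show with n = 10.**
- Mean change: 95% half-width = t(0.975, 9)/√10 = 2.262/3.162 = 0.72 SD of the change score.
- 0 of 10 worsened: exact two-sided 95% upper limit = 1 − 0.025^(1/10) = 30.8%.
- 1 of 10 worsened: exact 95% interval 0.3% to 44.5%.

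**The case against.** The strongest reply is that the adverse-event definition is broad. It takes in any new or aggravated symptom, with no threshold, and events are collected at the same post-implant visits as the scales. Section 7.3 reports maximum severity, serious events and discontinuations as well as counts. Sections 4.11 and 7.5 act on persistent worsening. A reader might infer that psychiatric harm would go unreported, or would appear only as present or absent; the documents do not support either reading. What survives is narrower: nothing requires a score change to be recorded as an event, so it may or may not appear.

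A reader might also infer that the scales were scheduled because these are named stimulation harms. That motive is not stated. The use the protocol gives for depression and anxiety changes is to guide programming, and the therapy-related examples in Section 8.3 name depression and suicidal ideation but not anxiety or mania.

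Nor does the appearance of depression and suicidal ideation under several headings in Section 8.3 show that attribution fails. Those lists are examples and allow case-by-case assignment. Change-from-baseline tables would not settle attribution either, since there is no control group.

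Finally, the GAF and the neurocognitive battery also lack a planned summary, and Section 7.4 is thin throughout. That is true and wider than this point, but it does not remove the gap for a primary objective.

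**Conclusion.** The point holds as a gap in the stated safety analysis. Section 7.3 defines the safety result from adverse events alone and leaves out the scored data on depression, anxiety, mania and suicidality: 310 scheduled ratings after lead implantation under the assumptions above. A shift handled by reprogramming may not appear in that result.

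How often this would happen cannot be estimated. The documents give neither a rate of such shifts nor the share that would be recorded as events, and any figure would rest on invented inputs. The conclusion does not need one. It rests on the text of Sections 7.1 to 7.5, on the absence of a score-to-event rule, and on the schedule in table 4.12. The change should be made because it concerns a primary objective and uses data already being collected. It would make the safety description complete; it would not show that stimulation caused any change.

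**What to change.** Add to Section 7.3, labelled descriptive:

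- Per-subject listings, and a summary at each later visit, of change in Ham-D, BAI and YMRS from the mean of Visits 1 to 3. Show Visit 5 separately from Visits 6-13, and reconcile Section 4.8 with table 4.12 on whether programming takes place at Visit 5.
- Each subject's largest worsening on each scale. Give a proportion with an exact interval only if the sponsor prespecifies a cutoff for worsening; without one, the maximum over nine visits would show some worsening in many subjects by chance.
- A listing of any post-implant ideation or behavior on the CSSS against Visits 1 and 3. Table 4.12 schedules no CSSS at Visit 13, so the scheduled ratings in this listing end at Visit 12.
- The Beck Youth Inventory reported separately for ages 15-17 and not pooled with Ham-D or BAI.

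The cost is a few tables, with no new visits, data or clinical rules. The downside is that, with 10 subjects and several scales, some changes will arise by chance and intervals will be wide, so the tables should carry no tests and no claim of effect.

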### 2. Objectives (include all primary and secondary objectives)

#### 2.1. Primary Objectives

- To evaluate the efficacy of DBS of the thalamic Ce-Spv-Voi complex on tic frequency and severity in 10 subjects with treatment-resistant Tourette Syndrome.
- To evaluate the safety of DBS of the thalamic Ce-Spv-Voi complex in 10 subjects with treatment-resistant Tourette Syndrome.

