A head CT examination immediately after the lead placement procedure will be obtained while the patient is still wearing the stereotactic frame (this is our standard procedure for other movement disorder DBS cases). This will allow us to check for hemorrhage, the amount of pneumocephalus, and lead placement. The operating room will be reserved, and the operative field kept sterile should the need arise to revise the

Date: 2/24/2021

Principal Investigator: [name], PhD

Application Number: NA\_00073086

lead positioning or evacuate a hemorrhage. The frame will be removed once the head CT examination is cleared by the operative surgeon.

A neurocritical care team will stabilize and monitor the patient in the postoperative period.

The required study documentation must be filled out by the neurosurgical team:

- Surgery Form
- Adverse events

After the subject is stable and discharged, the subject will be given an appointment card for the next study visit. **The neurostimulator will be implanted under the chest wall at the next visit.**

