## 8.2. Adverse events associated with DBS

There is a small but serious risk of intracranial hemorrhage with implantation of the lead, which is substantially lower than the risk associated with ablative procedures such as pallidotomy (39). A review of the literature estimated that rates of symptomatic and asymptomatic intracranial hemorrhage in DBS of the STN are ~ 2% and 1.2%, respectively (40) and infection occurs in ~ 2% of cases. The mortality rate for the procedure is below 1% and is mostly due to intracranial hemorrhage. One large multicenter report of 1,183 patients who received DBS reported a 30-day postoperative mortality rate of 0.4% (41). Other reported complications included hardware problems such as generator failure or lead breakage (6%—9/149), stimulation-induced side effects (3%—4/149), and behavioral changes (1%—2/149) (42). The infection rate is no higher than for other surgical procedures, but if it does occur, it can necessitate the explantation of the device or generator (43).

Deep brain stimulation can cause brain tissue damage if the stimulation charge density exceeds 30  $\mu\text{C}/\text{cm}^2/\text{phase}$ . The stimulation settings used in this study (similar to the current FDA approved DBS indications) will not exceed this limit.

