(passing through the microelectrode guide tube) and can aid in defining possible side effects due to the stimulation currents from the final implanted electrode and can guide the movement of the electrode on subsequent passes to optimize placement in the thalamus while minimizing sensory or motor side effects due to the applied stimulation.

Standard risk reduction efforts in the operating room will be implemented as in other surgical procedures. The federally mandated Safety Pause will be performed before skin incision, which includes patient verification, surgical site verification, and a team discussion of unusual case aspects. The equipment packs will be opened on the sterile field before skin incision to check for any sterility or operational issues. Intravenous antibiotics will be administered to the patient within 30 minutes of skin incision, followed by two postoperative doses for the stage of the procedure involving intracranial electrode placement. A single preoperative dose of antibiotics will be given within 30 minutes of skin incision for the implantation of the implantable pulse generator. Electrode placement will additionally be checked in the operating room using a fluoroscopic unit which has been draped into the field. A lateral fluoroscopic image will include the electrode tips and their location with respect to the frame fiducials showing the center of the frame coordinate system. Postoperative imaging will include an immediate head CT examination as the patient leaves the operating room, and a delayed MRI of the brain. Both scans are to verify final electrode location and to look for any perioperative complications (i.e. hemorrhage, lead migration / breakage).

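### Section 7.3 defines an adverse event by symptoms alone, which conflicts with Section 8.3 and leaves it unclear whether silent hemorrhages and device failures enter the safety tables

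*Combined protocol and SAP*

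**What the plan says.** Safety is one of two primary objectives in Section 2.1: "To evaluate the safety of DBS of the thalamic Ce-Spv-Voi complex in 10 subjects with treatment-resistant Tourette Syndrome".

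Section 7.3 is where the statistics section says how safety will be assessed. It records the frequency and severity of "adverse events, defined as any new symptom or worsening of a pre-existing symptom". The summaries follow from that term: "Adverse events reported on case report forms will be mapped to preferred terms and body systems", then subject counts and percentages, a table by worst severity, and displays of serious events and of events that lead to discontinuation. Signs, imaging findings and device malfunctions are not mentioned.

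Other sections look for, or name, events that can occur without a symptom:

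- Section 4.6, on the head CT immediately after lead placement: "This will allow us to check for hemorrhage, the amount of pneumocephalus, and lead placement".
- Section 8.2, on that CT and the delayed MRI: the scans are also to "look for any perioperative complications (i.e. hemorrhage, lead migration / breakage").
- Section 8.2 gives separate background figures, about 2% and 1.2%, for "rates of symptomatic and asymptomatic intracranial hemorrhage in DBS of the STN".
- Section 8.3 sorts adverse events into five categories. Its Device Related examples are "Lead fracture, lead migration, implantable pulse generator failure or abnormal function, skin erosion or delayed infection". Its Surgical/Procedure Related examples include cerebral hemorrhage. Neither list requires a symptom.

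The severity scheme at the end of Section 8.3 has a serious class and a moderate-or-severe class. The lower one begins with events that could get in the way of ordinary activity.

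**The concern.** The two sections answer the question of what counts as an adverse event differently. Suppose the post-operative CT shows a small hemorrhage in a subject who is clinically unchanged, or the MRI shows a displaced lead with no clinical effect. A coordinator who follows 7.3 can leave the event off the adverse-event form. One who follows 8.3 would enter it. Section 7.3 does not refer to 8.3 and plans no table by the 8.3 categories, so nothing tells the coordinator which section governs.

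The events in doubt are surgical and device harms particular to this procedure. With 10 subjects, one such decision moves a reported rate by 1/10, or 10 percentage points. A symptom-only reading can only lower the count. Section 7.6 also sends adverse-event information to an external registry, so inconsistent capture would travel beyond this study.

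**Working it through.** The point turns on wording. The arithmetic only shows how often the conflict could matter.

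**Step 1. Which events are in doubt**

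| Event | Under 7.3 | Under 8.3 |
|---|---|---|
| Hemorrhage with symptoms | counted | counted |
| Hemorrhage seen on imaging only | not counted | named as cerebral hemorrhage, no symptom condition |
| Lead migration, lead fracture or generator failure with symptoms | counted | counted |
| The same without symptoms | not counted | named as Device Related |

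Only the second and fourth rows are in dispute.

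**Step 2. Inputs**

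- n = 10 (Section 2.1).
- Asymptomatic hemorrhage: 1.2%, from a literature review of subthalamic stimulation (Section 8.2).
- Hardware problems such as generator failure or lead breakage: 9 of 149 (Section 8.2). The title of the cited source in Section 12 refers to the ventralis intermedius nucleus.
- Share of hardware problems that cause no symptom: not given. Call it s, between 0 and 1.

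**Step 3. Reproduce the protocol's figure**

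9/149 = 0.0604, which agrees with the stated 6%.

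**Step 4. Chance of at least one event in 10 subjects**, P = 1 − (1 − p)^10

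- Asymptomatic hemorrhage: 1 − 0.988^10 = 1 − 0.8863 = 11.4%. Expected subjects: 10 × 0.012 = 0.12.
- Any hardware problem: 1 − (140/149)^10 = 1 − 0.5363 = 46.4%. Expected subjects: 10 × 0.0604 = 0.60.
- Either, if independent: 1 − 0.8863 × 0.5363 = 52.5%. Expected subjects: 10 × (1 − 0.988 × 140/149) = 0.72.

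**Step 5. Range over the unknown share**

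Under a literal 7.3, the chance that at least one event is left out is 1 − [0.988 × (1 − s × 9/149)]^10.

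- s = 0: 11.4%.
- s = 0.5, for illustration only: 1 − (0.988 × 0.9698)^10 = 34.8%.
- s = 1: 52.5%, the ceiling.

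If 8.3 decides what goes on the form, nothing is left out and the figure is 0.

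**Step 6. Severity table**

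Section 7.3 tabulates events by worst severity. A silent finding that is not serious has no effect on activity and so has no clear place in the 8.3 scheme. Widening the definition alone would leave these events ungraded.

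**The case against.** The strongest reply is that 8.3 already covers the gap. It names every event type at issue as an adverse event, hemorrhage included. The 7.3 tables are built from whatever is reported on the case report forms, and Section 4.6 has the neurosurgical team complete adverse-event documentation at the lead-implantation visit, which includes the CT. Sections 4.9, 4.10 and 4.14 make the reporting of complications part of the purpose of later visits. An event recorded in this way reaches the tables. The scans are done regardless, and this is a small open-label pilot with descriptive safety summaries.

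Most of this stands. A reader might infer that silent hemorrhages and device failures are definitely excluded from the safety analysis. The documents do not support that, because 8.3 offers a route in. What the reply does not remove is the contradiction. The 8.3 lists classify events by cause and do not say that they replace the 7.3 definition. The adverse device effect definition in 8.3 does not settle it either: it is confined to serious or unanticipated serious problems, so an anticipated silent lead migration falls outside it. Whether the bare term cerebral hemorrhage reaches an incidental CT finding is also left open.

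A reader might also infer that silent events escape the stopping rule in Section 7.5. The documents do not support that either. The ground there is a significant event that jeopardizes patient safety, and it expressly extends to events related to the surgery or the stimulation, with no symptom condition. A finding that jeopardizes safety is covered; one that does not would fail that ground under any definition of adverse event.

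Finally, some hardware failures cause symptoms. A generator failure that lets tics return is a worsening of an existing symptom and already meets 7.3. This is why 52% is only a ceiling.

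**Conclusion.** The concern holds as an inconsistency between Sections 7.3 and 8.3 that leaves the handling of symptom-free events unsettled for a primary objective. Under a literal 7.3, the chance that at least one asymptomatic hemorrhage goes uncounted in 10 subjects is about 11%. Adding hardware problems takes it to at most about 52%. If 8.3 governs, the loss is zero.

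These figures assume that rates from other stimulation targets apply to this one, that hemorrhage and hardware problems are independent, and, for the ceiling, that every hardware problem is symptom-free. The documents give no lead-migration rate, so silent migrations are not separately allowed for.

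This is a correction worth making before the safety tables are produced. It does not show that data have been or will be lost, and it does not put the study's conduct in question.

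**What to change.** 1. In Section 7.3, define an adverse event as any new or worsened symptom, sign, imaging finding or device malfunction, whether or not it causes symptoms, and refer to Section 8.3 so that the two agree.
2. Add a class for asymptomatic or mild events to the severity scheme at the end of Section 8.3, so that the 7.3 severity table can place them.
3. Tabulate events by the five 8.3 categories, and show symptomatic and asymptomatic intracranial hemorrhage on separate lines.

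The cost is one revised sentence in 7.3, one added severity class, a symptomatic yes/no field on the adverse-event form and a table layout. No scans or visits are added. Reported event percentages may be slightly higher; the separate hemorrhage lines let a reader see how much of that comes from silent findings.
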